1 PROTOCOL SUMMARY

1.1 SYNOPSIS

Title: Utilizing Advances in Digital Inhaler Technology to Understand Heterogeneous Treatment Responses to Biologics in Severe Asthma

Study Description: This real-world study aims to determine baseline inhalation parameters and patterns of use in patients receiving treatment with TEVA digital inhalers, and to develop predictive models for asthma exacerbations and response to biologics using data collected from these devices.

Objectives:

Primary Objective:
To determine the baseline inhalation parameters and patterns of use of both the maintenance (AirDuo®) Digihaler™ and rescue (ProAir®) Digihaler™ in patients with severe persistent asthma who are being treated with biologics.

Secondary Objectives:

1. To determine the predictive value of inhalation parameters, including peak inspiratory flow (PIF), inspiratory time and volume, and number of inhaled doses on asthma exacerbations in a population of severe asthma patients on biologics.
2. To determine whether inhalation measurements can serve as surrogates of standard expiratory flow measurements. Specifically, to determine the correlation between PIF with FEV1 and identify thresholds for changes in PIF that are associated with a clinically meaningful increases or decreases (10%) in lung function as measured by conventional spirometry (e.g., FEV1).
3. To determine the impact of variable degrees of adherence to maintenance therapy on outcomes to biologics. The Digihaler™ will allow us to collect accurate information on adherence that will be utilized to divide patients into groups and to assess asthma outcomes such as change in mean FEV1, exacerbations, oral steroid reduction, and asthma control (using the asthma control test scores over time) in patients receiving biologic therapies.
4. To determine the impact on inhalation parameters on categorical response to biologics. Response will be categorized as non-response, partial and complete response on the basis of six factors: a 50% reduction in exacerbations, any reduction in maintenance OCS dose, change of at least 10% in FEV1, improvement of 3 points in ACT score, and patient perception of global improvement in asthma.

Exploratory Objectives

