3 OBJECTIVES AND ENDPOINTS

OBJECTIVES	ENDPOINTS	JUSTIFICATION FOR ENDPOINTS
Primary		

To determine the baseline inhalation parameters and patterns of use of both the maintenance (AirDuo®) and rescue (ProAir®) Digihaler™ in patients with severe persistent asthma who are being treated with biologics from baseline through the duration of the 12-month treatment period
	
 • Mean number of daily doses of ProAir® Digihaler™ • Mean number of daily doses of AirDuo® Digihaler™ • Median number of daily doses of ProAir® Digihaler™ • Median number of daily doses of AirDuo® Digihaler™ 	
The number of inhalations of rescue and maintenance bronchodilator use varies amongst and within patients with severe asthma and is impacted by changes in asthma control. This is a clinically meaningful measurement that is included in assessments of disease activity and control. PIF, inspiratory time and volume vary with changes in baseline asthma control and may be important in identifying acute exacerbations of asthma.
 
Maintenance therapies can impact asthma control and confound the response to biologics. In addition, the patterns of use of maintenance therapies and the potential discordance with rescue inhaler use would be important to delineate in this severe asthma population.

Secondary		

To determine the impact of variable degrees of adherence to maintenance therapy on outcomes to biologics. The Digihaler™ will allow us to collect accurate information on adherence that will be utilized to divide patients into groups and to assess asthma outcomes such as change in mean FEV1, exacerbations, oral steroid reduction, and asthma control (using the asthma control
	
 • Proportion of patients with different adherence rates. 
Tests: Summary, chi-squared test, and Tukey’s HSD test statistics of asthma outcomes by adherence group.
	
Adequate understanding of adherence is essential for guiding treatment decisions in clinical asthma care. It may impact response to biologics particularly in patients that are partial responders to targeted therapies. The degree of asthma control while on biologics may be altered by

OBJECTIVES	ENDPOINTS	JUSTIFICATION FOR ENDPOINTS

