
test scores over time) in patients receiving biologic therapies.
 
Definitions: Adherence rates will be defined as: high (>80% of puffs), moderate (50-80% of puffs) and low levels (<50% of puffs) of adherence to maintenance inhalers (assuming an expected baseline usage of two puffs per day).
		
non-adherence to inhaled therapies and lead to incorrect conclusion that the biologic is not effective. In addition, little is known about how patients with severe asthma utilize their inhalers once biologics are initiated and more importantly if it is safe to discontinue these therapies altogether.

To determine the impact on inhalation parameters on categorical response to biologics. Response will be categorized as non-response, partial and complete response on the basis of six factors: a 50% reduction in exacerbations, any reduction in maintenance OCS dose, change of at least 10% in FEV1, improvement of 3 points in ACT score and patient perception of global improvement in asthma.
	
 • Proportion of patients achieving non-response, partial and complete response to biologics. 
Tests: Summary, chi-squared test, and Tukey’s HSD test statistics of inhalation parameters by response group.
	
Response to biologics is heterogeneous, and it is unclear if inhalational parameters measured by the Digihaler™ are correlated with degree of response.

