8.1.2.6 PATIENT REPORTED OUTCOMES

Asthma Control Test (ACT)

The ACT captures asthma symptoms and short acting bronchodilator usage. Questions will be weighted equally and scored per the standardized questionnaire (REF). An ACT score of <19 is consistent with uncontrolled asthma.

Asthma Impairment and Risk Questionnaire (AIRQ)

The AIRQ™ is a patient assessment tool intended to help identify patients 12 years of age and older whose health may be at risk because of uncontrolled asthma. This assessment is based on a series of patient-facing questions about asthma medications, respiratory symptoms, and utilization of health care resources. Depending on the patient's responses to these questions, the patient will receive a score reflecting their level of asthma control.

St. George's Respiratory Questionnaire

The St. George's Respiratory Questionnaire (SGRQ) is a patient reported questionnaire designed to measure impact on overall health, daily life, and perceived well-being in patients with obstructive airways disease. Scores range from 0 to 100 with higher scores indicating more limitations.

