9.4.3 ANALYSIS OF THE SECONDARY ENDPOINT(S)

1. To develop an algorithm that can identify probable imminent exacerbation events using Digihaler™ inhalation parameter measurements, we will compare the performance of several different machine learning regression models. Since we expect our training set to be relatively small with a low event rate, we plan to use the entire inhalation parameter dataset for model training but will employ repeated k-fold cross-validation to reduce variance (over-fitting) and include non-linear features to reduce bias (under-fitting). Examples of features that could be computed and included in this model include but are not limited to: difference between current value and patient-specific 7-day moving average, difference between current value and patient-specific 24-hour moving average, 7-day sample entropy, 24-hour sample entropy, difference in Min-Max over last 24 hours, etc.

A logistic regression model would treat the outcome (exacerbation) as a binary (Yes/No) event. The output of this model would be a daily probability between 0 and 1 that an exacerbation event will occur within a certain period of time. Different models will be fit for different periods of time (e.g., 24, 48, 72 hours) and the performance of each model assessed and compared to others. A recurrent event survival model would treat the exacerbations as discrete events in time. The output of this model would be the predicted time (e.g., in decimal days or hours) until the next event. Other models may include convolutional and/or recurrent neural networks (RNN) with LSTM or GRU architecture with varied numbers of hidden layers.

2. To determine whether and how PIF is associated with FEV1 and FVC, we assess the linearity and strength of the relationship using scatter plots, calculate the paired correlations (Pearson, Kendall, and Spearman), and compute univariate linear regression equations with PIF as the predictor and FEV1 or

FVC as the response. If non-linearity is found, we will determine the appropriate PIF transformation or polynomial term to use in the regression. Regression summary statistics (e.g., R-squared, Mean Absolute Error, Coefficients, and p-values) will be reported.

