3. Patients will be assigned to one of three adherence groups (low, moderate, high) based on Digihaler™ inhalation usage parameters over the previous month. We will use the Chi-squared test to determine if group differences exist for each asthma outcome over the next month, and Tukey's Honest Significant Difference test to determine which groups are significantly different.

4. Patients will be assigned to one of three biologics response groups (non, partial, complete) based on six asthma factors (described earlier). We will use the Chi-squared test to determine if group differences exist for each inhalation parameter, and Tukey's Honest Significant Difference test to determine which groups are significantly different.

5. To develop an algorithm that can predict patients that will respond to biologics regression or classification models. Since we expect our training set to be relatively small with a low event rate, we plan to use the entire inhalation parameter dataset for model training but will employ repeated k-fold cross-validation to reduce variance (over-fitting) and include non-linear features to reduce bias (under-fitting). We do not know a priori whether regression or classification would be the appropriate approach to this question so we will test models using both approaches. The classification approach can be formulated as either a two-class problem – Non vs. Partial or Complete responders, or Non or Partial vs. Complete responders – or a three-class problem – Non vs. Partial vs. Complete. The regression approach requires a two-class formulation using logistic regression. Different models will be fit for different formulations and the performance of each model assessed and compared to others.

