9.4.9 EXPLORATORY ANALYSES

We plan to conduct extensive exploratory analyses including but not limited to: data cleaning and aggregation, outlier analysis, multicollinearity (correlation) analysis, sex effect analysis, age effect analysis, time series analysis, unsupervised cluster analysis, univariate testing (T-tests, Fisher's Exact Test, Wilcoxon Test, Chi-Squared Test, Tukey's Honest Significant Difference (HSD) Test), multivariable linear and non-linear regression, feature creation and selection for machine learning models, feature scaling and centering, training machine learning models using repeated k-fold cross-validation, and extensive data visualization for correlations and time series analysis.

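### Section 9.4.3 item 4 tests continuous inhalation parameters with a chi-squared test and gives no categories; item 3 does not say which form of each outcome its chi-squared test uses

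*Combined protocol and SAP*

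**What the plan says.** Section 9.4.3 item 4 places patients in three response groups (non, partial, complete) and continues: "We will use the Chi-squared test to determine if group differences exist for each inhalation parameter". Tukey's HSD is then named to find which groups differ. Item 3 has the same structure for low, moderate and high adherence: "We will use the Chi-squared test to determine if group differences exist for each asthma outcome over the next month", again with Tukey's HSD.

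The table in section 3 repeats the pairing of chi-squared and Tukey. The adherence row ends "HSD test statistics of asthma outcomes by adherence group" and the response row ends "HSD test statistics of inhalation parameters by response group". The response-group analysis appears there twice, once as secondary and once as exploratory.

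On the scale of these quantities:

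- Section 9.4.2 summarises PIF, inspiratory time and inspiratory volume per inhalation, using mean, SD, median and IQR.
- Secondary objective 3 in the synopsis (section 1.1) will "assess asthma outcomes such as change in mean FEV1, exacerbations, oral steroid reduction, and asthma control", the last of these through ACT scores over time.

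Neither item 3 nor item 4 gives a cut-point or a categorisation rule.

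**The concern.** A chi-squared test of group differences compares the distribution of categories between groups. PIF, inspiratory time and inspiratory volume have no categories in this plan. For PIF, thresholds for change are something the study sets out to find. The analyst must then either cross-tabulate the raw values, which tells nothing about the groups, or choose a split after the data are in, which loses power and is not pre-specified.

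Hypotheses 3 and 4 in section 9.1 (outcomes by adherence group, inhalation parameters by response group) rest on items 3 and 4. In both items chi-squared is the test given the job of deciding whether any group difference exists.

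**Working it through.** **Inputs.** N = 100, PIF mean 115 and SD 15 (section 9.2). Alpha 0.05 (section 9.4.1), taken two-sided and without Bonferroni. Group sizes 12/48/40, from the background figures in section 2.1 (10-15% non-response, 40% complete response, remainder partial). The plan gives no effect size for items 3 and 4, so equal steps of 5, 7.5 and 10 PIF units between adjacent groups are assumed. The data are normal with one value per patient.

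**The plan's own figure.** The half-width of the 95% CI for mean PIF is 1.96 × 15/√100 = 2.94, which rounds to the stated 3. It reproduces and is not affected by this point.

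**Chi-squared on distinct values.** With k groups of sizes n_g and N distinct values, the table is k × N with one patient per column.

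- Expected count in group g, any column: n_g/N.
- Each patient in group g contributes O²/E = N/n_g. Summed over patients this is Σ n_g × N/n_g = kN.
- Chi-squared = kN − N = N(k − 1) = 100 × 2 = 200.
- Degrees of freedom = (N − 1)(k − 1) = 99 × 2 = 198.
- p = 0.447.

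Neither the values nor the group sizes remain in the result. Simulated data sets with outer group means 30 units (2 SD) apart returned the same 200 on 198 df. If PIF were recorded in whole units (an assumption, since no resolution is given), ties would free the statistic, but power would be only about 3%, 5% and 10% at the three steps.

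**ANOVA, exact.** For step 7.5 the group means are 0, 7.5 and 15 relative to the first group.

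- Weighted mean = (48 × 7.5 + 40 × 15)/100 = 9.6.
- Between-group sum of squares = 12 × 9.6² + 48 × 2.1² + 40 × 5.4² = 2484.
- Noncentrality = 2484/15² = 11.04.
- Critical F(2, 97) = 3.09, so power = 84%.

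Steps 5 and 10 give noncentrality 4.91 and 19.63, with power 48% and 98%.

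**The other tests, by simulation** (3000 to 6000 replicates per setting; ranges are across repeat runs):

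| Test | Step 5 | Step 7.5 | Step 10 |
|---|---|---|---|
| ANOVA | 48-49% | 84-85% | 98% |
| Tukey's HSD, any pair | 46-47% | 81-83% | 97-98% |
| Chi-squared after median split | 34-35% | 64-66% | 87-89% |
| Chi-squared, distinct values | 0% | 0% | 0% |

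Kruskal-Wallis gives 45% and 82% at steps 5 and 7.5. Varying the group mix from 10/50/40 to 15/45/40 at step 7.5 gives ANOVA 80-87% and median-split chi-squared 60-68%, so the ordering does not depend on the mix.

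**Item 3, outcome by outcome.** A categorical form exists elsewhere in the documents for each named outcome:

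- FEV1: a change of at least 10% (response definition, sections 1.1 and 3).
- Oral steroids: any reduction in maintenance dose (same place).
- ACT: "An ACT score of <19 is consistent with uncontrolled asthma" (section 8.1.2.6).
- Exacerbation: yes/no (section 9.4.3 item 1).

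None of these is tied to the item 3 test. For the binary forms chi-squared is suitable, and Tukey's HSD, which compares means, is the mismatched half. For FEV1 change or ACT score as numbers, the mismatch is as in item 4.

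**The case against.** **Tukey already answers the question.** This largely stands. Tukey's HSD controls the familywise error without an omnibus test in front of it, and on one mean per patient it gives up only one to four points of power against ANOVA in the table above. Section 3 lists summary, chi-squared and Tukey side by side as outputs, and no text makes Tukey depend on chi-squared. Section 9.4.5 also promises summaries by adherence and response group, so the group means would be visible whatever chi-squared returned. A reader might infer that the plan cannot detect a difference in inhalation parameters, or that Tukey is gated. The documents support neither. The wording (one test for whether groups differ, the other for which) can still be read as a sequence, so the plan should say.

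**Chi-squared may be shorthand for Kruskal-Wallis,** whose statistic is referred to that distribution. The text does not support this. Kruskal-Wallis is never named, and section 9.4.9 lists chi-squared as a test in its own right: "univariate testing (T-tests, Fisher's Exact Test, Wilcoxon Test, Chi-Squared Test", followed by Tukey's HSD.

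**Nobody would build a 3 × 100 table.** Perhaps not, and the plan does not say that one would be built. But it names no other table, and an unplanned split is the costly alternative shown above.

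**Item 3 has usable categories.** This stands. A reader might infer that item 3 is invalid throughout. It is not: what is missing is the link between each outcome's form and its test.

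**Conclusion.** Item 4 is wrong as written. It assigns the decision on group differences in three continuous parameters to a test that needs categories the documents do not supply. The fixed result (200 on 198 df, p = 0.447) requires only that the 100 patient values be distinct. The loss from a rescue by median split, about 20 percentage points at step 7.5, rests on the assumed step, normal data and the 12/48/40 mix.

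The practical harm is limited. If Tukey's HSD is run regardless, a sound comparison sits beside an uninformative p-value. Only if it is run solely after a significant chi-squared would a real difference be missed, and the plan states no such rule. Item 3 shares the fault only for FEV1 change and ACT score analysed as numbers. All of this concerns secondary analyses, one of them also listed as exploratory. It should be fixed before analysis.

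**What to change.** - **Item 4, and item 3 for numeric FEV1 change and ACT score:** replace chi-squared with one-way ANOVA (or Kruskal-Wallis) on one summary value per patient, followed by Tukey's HSD (or Dunn's test). State that the pairwise comparisons are not conditional on the omnibus result.
- **Item 3, binary outcomes:** name the binary form of each outcome. Keep chi-squared or Fisher's exact test with one row per patient, and replace Tukey's HSD with multiplicity-adjusted pairwise comparisons of proportions.
- **Section 3:** make the same changes in the adherence row and in both the secondary and exploratory entries for the response groups.

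The cost is SAP wording and standard R functions. No new data are needed.

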12. Machine learning model developed for predicting responders to biologics (developed in collaboration with the University of Michigan Morphomic Analysis Group). Reporting key factors in the model that are associated with response, using inhalation parameters (digital markers), clinical factors, and biomarkers.

Study Population: Adults > 18 years of age or older with severe persistent asthma as defined by ERS/ATS criteria that are currently receiving or awaiting approval for biologic therapies for asthma.

Phase: Open Label Real World Study

[figure not shown]
Description of Sites Enrolling Participants: All patients will be recruited from the Michigan Medicine Severe Asthma Clinics.

Description of Study Intervention: Maintenance inhaler (AirDuo® Digihaler™) and two rescue inhalers (ProAir® Digihaler™) use in Severe Asthma patients currently receiving or awaiting approval for biologic therapies for asthma.

Study Duration: 2 years, including approximately 3-month start-up, 6 months' recruitment period, 12 months follow-up of the last subject in (LSI), 3-month data cleaning and analysis.

Participant Duration: 12 months

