4 STUDY DESIGN

4.1 OVERALL DESIGN

This is an open-label real world study that has been designed to determine the patterns of use and impact of inhalation parameters on both predicting asthma exacerbations and response to biologics in patients with severe asthma. The digital inhalers used in this trial are unique in their ability to seamlessly record multiple parameters as the patients use their inhalers. There are no external devices required for device use recording. We aim to leverage the information collected by the digital inhaler to understand the impact of exacerbations on inhalation parameters, to determine the clinically meaningful differences in these measurements, and to determine their correlation to FEV1, which is the most widely accepted measure of airflow in patients with severe asthma. Home spirometry is challenging and expensive and if inspiratory flow measures can be used as surrogates of expiratory flow, this would revolutionize our ability to track lung function in patients with severe asthma. The digital parameters will be incorporated with clinical, digital, and biological markers in an attempt to identify predictive algorithms that can identify responders to biologics early in the treatment course, facilitating decisions about continuation or discontinuation of therapy.

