9 STATISTICAL CONSIDERATIONS

9.1 STATISTICAL HYPOTHESES

- Primary Efficacy Endpoint(s): Establish group-level daily/weekly baseline normative values for: (1) mean and median number of doses of ProAir® Digihaler™ and AirDuo® Digihaler™, and per-inhalation baseline normative values for (2) peak inspiratory flow (PIF), (3) inspiratory time and (4) volume. We will test the hypothesis that patient-specific baseline usage values are significantly different from usage values collected during or leading up to exacerbation events.
- Secondary Efficacy Endpoint(s): 1. Test the hypothesis that imminent exacerbation events can be predicted using Digihaler™ inhalation parameter measurements. 2. Test the hypothesis that PIF is linearly (or non-linearly) related to FVC and FEV1. Test the hypothesis that there exists a threshold for change in PIF that is associated with a clinically meaningful change (>10%) in lung function. 3. Test the hypothesis that patients with low, moderate, and high adherence to maintenance inhalers have significantly different asthma outcomes. 4. Test the hypothesis that non-responders, partial, and complete responders have significantly different Digihaler™ inhalation parameters. 5. Test the hypothesis that future response to biologics can be predicted using clinical, biological, and digital (inhalation) markers.

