9.4 STATISTICAL ANALYSES

9.4.1 GENERAL APPROACH

We will perform a retrospective analysis of prospectively enrolled patient data. Following completion of the study's data collection period, data from the Digihaler™ asthma inhalers will be downloaded to secure servers, joined to clinical data from the electronic medical record (including exacerbation event data) and patient questionnaire responses, and analyzed using R statistical analysis software. The University of Michigan Morphomics Analysis Group will collaborate with the TEVA analytics team to produce a rigorous and reproducible research result. An alpha level of 0.05 will be used to determine "statistical significance" with a Bonferroni correction ($\alpha / \# \text{ tests}$) applied to account for multiple testing when appropriate.

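### The model for future response to biologics (Section 9.4.3 item 5) sets no time zero, predictor window or response-scoring window, so look-ahead is not excluded

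*Combined protocol and SAP*

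**What the plan says.** **The aim is about timing.** Secondary hypothesis 5 in Section 9.1 reads: "Test the hypothesis that future response to biologics can be predicted using clinical, biological, and digital (inhalation) markers". Section 4.1 describes "predictive algorithms that can identify responders to biologics early in the treatment course", to support decisions on continuing or stopping therapy.

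**The analysis text is silent on timing.** Item 5 of Section 9.4.3 expects a small training set and says "we plan to use the entire inhalation parameter dataset for model training", with repeated k-fold cross-validation. It does not say when the clock starts, when predictors stop, when response is scored, or whether folds are split by patient.

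**The outcome has no date.** The Synopsis states: "Response will be categorized as non-response, partial and complete response on the basis of six factors: a 50% reduction in exacerbations". It lists further factors, among them a 3-point gain in ACT. Neither the Synopsis, Section 3 nor item 5 gives an assessment date or window.

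**All months will be to hand.** The Synopsis gives "Participant Duration: 12 months". Section 9.4.1 says: "Following completion of the study's data collection period, data from the Digihaler™ asthma inhalers will be downloaded to secure servers". Section 5.1, criterion 3, admits patients already on a biologic as well as those about to start one.

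**The concern.** A model that predicts future response needs predictors observed before the outcome. Nothing in item 5 secures that order. An analyst who followed it as written could summarise inhaler data over the whole follow-up and use that summary to classify patients whose response had already been reached, or was being reached, in the same months.

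Some overlap is built in. Section 8.1.2.6 says of a response factor: "The ACT captures asthma symptoms and short acting bronchodilator usage". Rescue doses are also a digital marker, so concurrent rescue use can partly restate the outcome. Exacerbation reduction is another response factor, but the 14-day exclusion around exacerbations in Section 9.4.2 covers only the normative baseline.

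For patients already on a biologic at entry, response may predate every inhaler record, and future response then has no starting point.

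At stake is what the AUROC means. A model that recognises a response already present may discriminate well and still say nothing useful about a decision early in treatment.

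**Working it through.** **1. Time order within Section 9.4.3**

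| Item | Predictor time | Outcome time |
|---|---|---|
| 1 (exacerbation) | current values, with 24-hour and 7-day features as examples | forward horizons such as 24, 48, 72 hours |
| 3 (adherence) | previous month | next month |
| 5 (response) | not stated | not stated |

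Items 1 and 3 order time; item 5 does not. The nearest text elsewhere is the exploratory objective in the Synopsis and Section 3: early changes predicting long-term improvement, in patients starting a first biologic or switching. It gives no week or month for either term. The 4 to 6 months in Section 2.1 describes current practice, not a study rule.

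**2. Does cross-validation help?** No. The left-out patients carry features from the same months as the training patients, so look-ahead is present on both sides of each split. If folds were split by inhalation or day, one patient could also fall on both sides.

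**3. The plan's own AUROC statement (Section 9.2: 100 patients, 50% events, AUROC 0.65).** The Hanley-McNeil variance is [A(1−A) + (n1−1)(a−A²) + (n0−1)(b−A²)] / (n1·n0), with a = A/(2−A) = 0.4815 and b = 2A²/(1+A) = 0.5121 at A = 0.65.

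- 50 vs 50: (0.2275 + 49×0.0590 + 49×0.0896)/2500 = 0.00300, so SE = 0.0548.
- 95% CI: 0.65 ± 1.96×0.0548 = 0.543 to 0.757. This excludes 0.5, so the plan's statement reproduces.

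The statement concerns precision only. It does not address when the predictors were measured.

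**4. Illustration of possible size (all inputs assumed).** Take 12 monthly values and 50% responders. Months outside the scoring window carry no information. Each of k months inside it correlates r with the latent response. The 12-month mean then correlates kr/√(k²r² + 12 − kr²) with the latent response. For k = 6 and r = 0.2 this is 1.2/√13.2 = 0.33. AUROC by simulation:

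| Scoring months used | r = 0.1 | r = 0.2 | r = 0.3 |
|---|---|---|---|
| 0 (landmark kept) | 0.50 | 0.50 | 0.50 |
| 3 | 0.54 | 0.58 | 0.62 |
| 6 | 0.58 | 0.65 | 0.71 |
| 9 | 0.61 | 0.71 | 0.79 |
| 12 | 0.65 | 0.77 | 0.85 |

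**5. Dependence on the assumed model.** Take 100 patients, 40% responders, response scored on months 7 to 12, a noisy monthly inhaler feature, and latent control with lag-1 correlation 0.5 to 0.85.

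| Share of latent variance stable within patient | AUROC, first 2 months | AUROC, all 12 months |
|---|---|---|
| none | 0.50 to 0.61 | 0.73 to 0.83 |
| 30% | about 0.63 to 0.68 | 0.82 to 0.88 (30% and 50% rows together) |
| 50% | about 0.70 to 0.73 | as above |

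The full-follow-up feature scores higher in every case, but the early AUROC depends heavily on the assumption.

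**6. Precision in a smaller subgroup.** The documents do not give the number of initiators and switchers. If it were 30, split 15 vs 15 (an assumption), the variance is (0.2275 + 14×0.0590 + 14×0.0896)/225 = 0.01026 and SE = 0.1013. The 95% CI at 0.65 is then about 0.45 to 0.85, which includes 0.5.

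**The case against.** The strongest reply is that the quoted phrase is not about time. It follows a remark that the training set is small and leads into cross-validation, so it mainly explains why there is no hold-out set. The same sentence stands in item 1, which does set forward horizons. That reading is fair. A reader might infer that the sponsor has decided to use inhaler data from the response period; the documents do not show such a decision. What stands is that no text rules it out.

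A reader might also infer that response is scored over the same 12 months as the inhaler data. No section says so. The fault is an undefined time frame, not a demonstrated overlap.

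Third, the protocol already separates an early-change algorithm and limits it to initiators and switchers. That deserves credit, and the fix builds on it. But the restriction has no dates and is not carried into item 5.

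Finally, the stakes are limited. The Synopsis and Section 3 list the machine-learning model as exploratory, although Sections 9.1 and 9.4.3 place it under secondary endpoints. Section 2.1 leaves the test of early prediction to future trials. The primary analysis and its sample-size basis are untouched. This bears on how much weight the point carries, not on whether it is right.

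**Conclusion.** The point holds as a gap in the written plan. Item 5 claims prediction of future response but fixes no time zero, predictor window or scoring window, so data concurrent with or later than the response can serve as predictors. Under that wording, an AUROC above 0.65 would not by itself show early prediction.

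The size of any inflation cannot be derived from the documents, which give neither a scoring window nor any correlation between inhaler features and response. The simulated values show only that the 0.65 figure can be reached without early information under some assumptions. They do not support the further inference that early inhaler data hold no usable signal: with a stable patient component, the early AUROC rises to 0.63 or more.

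**What to change.** In Section 9.4.3 item 5:

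- Set time zero at biologic start or switch.
- Limit predictors to data up to a stated landmark, chosen by the sponsor before analysis.
- Score response only on data after the landmark, in a stated window.
- Split cross-validation folds by patient.
- Fit this prediction model in the initiator/switcher subgroup already named in the Synopsis and Section 3.
- Report any model that uses full follow-up, or patients already on a biologic at entry, as association and not prediction.

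In Section 9.2, do not apply the 100-patient, 50%-event precision statement to this subgroup. Restate it for the subgroup's actual size and event rate.

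The change needs new analysis-plan wording and revised feature-building code, but no new data or visits. Its price is a probably lower AUROC, a shorter outcome window and fewer patients in the prediction model. Inhalers are first dispensed at baseline, so patients already on a biologic have no pre-biologic inhaler data and, unless they switch, cannot contribute to it.
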